After the participants complete the initial education modules and pre-surveys have finished, the study staff will set up the automated, one-way text program. Mothers and their participating partners will receive a \$25 pre-paid gift card following the initial survey completion, a second \$25 gift card following the 6-week follow up survey completion, and a third \$25 gift card following the 6-months follow up survey completion. Therefore, each participant is eligible for a total of \$75 in gift cards if they complete all surveys (\$150 total per couple).

4. Intervention:

Happy Health Loved (Experimental Condition). The HHL program is comprised of the three topical areas described in Table 2. This information will be delivered via tablet to both parents during the postpartum hospital stay. For the next 6 weeks text messages (4 per week) mapping closely with the tablet content will provide reminders, resources, and encouragement associated with the three areas of education. Based on participants’ responses in the tablet program, the messages will be personalized to the motivations, preferences, and concerns that parents indicate in the tablet program. Example content is provided in Figure 2. All program delivery will be managed through contracted partnership with 3C Institute (OhioHealth approved), specializing in behavioral health platforms using HIPAA-compliant procedures. 3C Institute is an award-winning research and development company founded in 2001 that brings research to practice to improve the health and well-being of people. The Institute creates, test and disseminates evidence-based programs and has received the Tibbetts Award from the Small Business Administration for technological excellence in 2014. 3C provides the platform for the tailored, automated text messaging for the study.

Table 2: Outline of HHL goals and activities

	Goals	Example Activities
modeling & feedback	Viewing breastfeeding as learned skill	Other mothers’ modeling of challenge management
	Reflecting on successes and growth	Accomplishment feedback on breastfeeding success
partner support	Increase perceived support	Prompt partner to show active support
	Mutual support of self-care	Prompts to both partners to mutually support self-care
stress coping	Behavioral activation	Prompt mother’s preferred rewarding activity
	Realistic expectations of self	Strategies for challenging negative thoughts

Participants will be asked one yes/no question each week (“still breastfeeding? Text Y for yes, N for no”). Once a “no” response has been received from a participant, all remaining text messages will emphasize coping and partner support only rather than breastfeeding, in order to minimize any guilt or distress a mother may feel for discontinuing breastfeeding. This will occur automatically within the program.

Data security. Participants assigned to the intervention condition will complete questions and activities within the online platform of Happy Healthy Loved, delivered on the HIPAA compliant, secure, encrypted platform delivered by 3C Institute (see support letter for details).

We will obtain survey data from mothers and their partners via online questionnaires completed using OhioHealth approved REDCap software (<https://www.project-redcap.org/>). Participants will complete the surveys using iPads provided by the research team.

Only the Principal Investigator (PI) and certain members of the research staff (e.g., study coordinator) will know of or have access to the participants' identities. Privacy and confidentiality will be maintained by assigning a study number to each participating mother-partner dyad. HIPAA compliant, password protected REDCap database will be used to store participant survey information. Only approved study personnel will have access to study data and individually identifiable private information about human subjects. All study personnel with access to study data will be certified to conduct research with human subjects, and will be aware of the importance of maintaining strict confidentiality. REDCap and 3C Institute intervention data will not be linked online; rather, the four-digit participant ID number will be the only link between the two sources of information. REDCap and the 3C Institute platform will be password protected, and accessing the iPad without the correct password would not allow an unauthorized person to access participant data.

The content and delivery of the text-message follow up will map closely with the content provided in the tablet-based materials. The intention is to provide reminders, resources, and encouragement associated with the three areas of education. Texts will be matched to mothers' response to questions in the educational module designed to identify her strengths and preferred coping strategies. For example, a mother who identified during the initial module that walking has been a positive coping strategy for managing stress and mood in the past would get a text specifically encouraging her to make time for a walk, with or without baby. The partner would receive a corresponding text suggesting that walking is helpful for the mother, and encouraging the partner to provide support for this activity in one of two ways: offer to watch the baby while mother walks or go for a walk with the mother and baby. Messages will be sent four times per week.

Learning to Breastfeed

The kinds of encouraging, understanding things you'd want a friend to say to you are the same things that are helpful to say to yourself. It might seem simple, or silly---but having an encouraging thought in your mind can be really powerful! Which one do you think you could use if you experience breastfeeding challenges?

Mom: Check items below to select.

Right now I'm frustrated, but I can do this.

Every time we try, we learn. I can stick with it.

We're both still getting the hang of this, and I'm doing my best!

I'm up for the challenge, and it will get easier.

none of these

Mom text:

When breastfeeding gets tough, encouraging thoughts can help. Try "We're both still getting the hang of this, and I'm doing my best."

Partner text:

Moms who feel supported by their partners are more likely to keep breastfeeding. Ask her how it's going and how you can help.

Figure 2. Example in-hospital tablet and follow-up text from Happy, Healthy, Loved program

Participants will be instructed on how to unsubscribe from the program at any time using a text response of "unsubscribe." Participants who unsubscribe will still receive the 6 week survey and will be contacted by the research team to learn whether they would like to withdraw from the study entirely or simply unsubscribe from the messages.

Control group activities. The control group activities consist of usual care at the RMH, GMC, and DH care sites. The videos are part of the subscription program The Newborn Channel, and parents can choose videos on demand to watch on topics covering a variety of topics from postpartum depression to safely bathing a newborn and recovery steps post-cesarean section. Control group participants will document with a signature after they have watched Newborn Channel videos on breastfeeding, infant care basics, and postpartum depression (currently required of mothers before hospital discharge). The control group participants will be sent four text messages per week for the first six weeks as well, but the content of the texts will be non-breastfeeding related. The content will instead summarize infant development facts. The text messages will be sent in order to separate the effect of receiving text messages from the effect of the active intervention content.

5. Confidentiality and Data Management:

3C Institute privacy protections are included as an appendix detailing specific technology safeguards. All study personnel will be trained in ethical conduct of research and data will be protected in the REDCap and 3C Institute platforms. Participants would be informed immediately if such a breach were to occur and we would take every effort to recover and protect the information. 3C Institute specializes in mental health education and support applications, and has a history of creating secure platforms for individual use that are HIPAA compliant. OhioHealth Information Security (IS) is reviewing the 3C contract and platform to ensure privacy protections meet OhioHealth strict IS security mandates.

All paper informed consent documents and study log book materials will be stored in a locked file cabinet at each hospital location within a secured room in the maternity floor. The approved study staff will hold the key to the file cabinet.

E. Statistical Analysis

The intervention's impact on the study's primary outcomes will be evaluated using intent-to-treat analysis with multiple imputation for missing follow up cases. Outcomes, adjusting for baseline variables, will be analyzed using ANCOVA for continuous variables (self-efficacy, partner support, and coping) and logistic regression for categorical variables (exclusive breastfeeding). To examine the extent in which increased partner support, and lower levels of stress would explain the effects of the intervention, two criteria will be used to establish whether there is statistically significant mediation in the model (MacKinnon, Lockwood, Hoffman, West, & Sheets, 2002; MacKinnon, Fairchild, & Fritz, 2007) including the joint significance of paths a (i.e., the path from predictor to mediator) and b (i.e., the path from mediator to outcome variable) and the asymmetric distribution of the product confidence interval test for the product ($a*b$) of the coefficients a and b , which have both shown the best combination of power and avoidance of type 1 error compared to 12 alternative tests of mediation (MacKinnon et al., 2002; MacKinnon et al., 2007).

We will use the regression-based approach described by Hayes to develop models that allow us to evaluate mediation (Hayes, 2008). The bootstrapping resampling method available in this approach provides an opportunity to run analyses that will approximate the sampling distribution to obtain confidence intervals (CIs) when variables are not normally distributed. With regards to aims 3 and 4, regression (logistic regression for dichotomous outcome variables) analyses controlling for relevant covariates will be used to examine relations between hair cortisol levels and partner support, coping, self-efficacy, and breastfeeding rates. Because both high and low levels of cortisol have been indicated as signs of dysregulation (Miller, Chen, & Zhou, 2007), a quadratic term will be added to the model to examine non-linear relationships. In addition, to these analyses, we will also use the mediation approach described above to explore the extent to which maternal mood may mediate the relations between cortisol and breastfeeding behaviors.

III. REFERENCES

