The intervention emphasizes three behavioral targets: a) providing resources to support breastfeeding through modeling, information, and feedback (tailored to maternal reported breastfeeding challenges and motivations); b) providing prompts to mother and partner to communicate about support strategies (tailored to parents' preferred support behaviors); and c) providing prompts for positive evidence-based coping strategies (tailored to parents' preferred coping activities). Exclusive breastfeeding as well as breastfeeding self-efficacy will be measured at 6 weeks and 6 months as primary outcomes. Secondary outcomes of coping behaviors and perceived partner support are the behavioral targets that are hypothesized to influence the primary outcomes of BSE and exclusive breast feeding and will also be measured at 6 weeks and 6 months. Because the intervention emphasizes coping strategies for managing stress, we hypothesize that baseline cortisol will act as a moderator for the intervention, with mothers experiencing elevated cortisol benefitting the most from the intervention.

In 2017, we conducted a small pilot study to test the feasibility of our HHL program. We enrolled 17 mothers and 10 partners to complete the baseline assessments and then randomly assigned them to the HHL group (n=8 mothers) or usual care (n= 8 mothers). Follow-up rates at 6-weeks postpartum were 94% for mothers and 90% for partners. Mothers and partners who completed the HHL intervention (n=12) rated the acceptability of the program on a five-point agreement scale. The majority of parents agreed or strongly agreed that the program was beneficial (83%) and that participating was manageable (91.7%). No parents opted to stop receiving messages during the six-week delivery.

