Primiparous, breastfeeding women living with a partner will be recruited directly on the maternity floors of three OhioHealth hospitals, Riverside Methodist Hospital (RMH), Grant Medical Center (GMC), and Doctors Hospital. Based on our pilot data, we plan to enroll up to 200 mother-partner pairs over a 24-month period. Based on Cohen's standard power functions, 80% power to detect a medium-large effect in outcomes ($\alpha = .05$) should be achieved with 64 participants per arm, leading to the proposed plan of a minimum of 60 couples per arm (Cohen, 1992). Assuming a conservative 25% attrition rate to achieve a final number of 128 couples, as well as the possibility that one member of a couple ends participation while the other continues, we estimate needing to enroll between 160-200 couples. Therefore, we will enroll up to 200 mother-partner pairs during the study period of September 1, 2020 and September 1, 2022.

1. Inclusion criteria includes primiparous mothers:
 - a. over the age of 18 years old,
 - b. living with a partner or spouse
 - c. have an intention to breastfeed their infant for at least 6-weeks postpartum;
 - d. whose infant is not in the Neonatal Intensive Care Unit,
 - e. have a mobile phone with text message capability,
 - f. have no current self-reported depressive episode, and;
 - g. English as a primary language
2. Exclusion criteria include mothers who:
 - a. have other biological children (past breast-feeding experience),
 - b. have infants in the Neonatal Intensive Care Unit,
 - c. do not have a mobile phone with text message capabilities,
 - d. report current episodes of depression, or are receiving antidepressant treatment or psychotherapy for depression,
 - e. have initial study survey that indicates suicide risks (participants who are identified as suicidal ideation at 6 weeks or 6 months will receive further assessment and referral but not be excluded from the program because it may be more harmful and penalizing to remove them from the program if they find it helpful. We will remind the participant that continuing is voluntary and there is no penalty if they wish to discontinue participation)
 - f. do not speak, read and write English

B. Aims and Hypotheses:

Aim 1: Investigate the efficacy of mobile-delivered breastfeeding self-efficacy program on

breastfeeding rates and breastfeeding self-efficacy, as compared to care as usual.

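### Minor: the stated minimum of 60 couples per arm and the lower enrolment figure of 160 fall short of the plan's own target of 64 per arm (128 couples) at 25% attrition; the ceiling of 200 meets it

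*Combined protocol and SAP*

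**What the plan says.** Everything bearing on this point is in the sample size paragraph of section II.A, Study Population. For 80% power at alpha 0.05 and an effect described only as medium to large, the paragraph says the power "should be achieved with 64 participants per arm, leading to the proposed plan of a minimum of 60 couples per arm". It then allows for loss to follow-up: "Assuming a conservative 25% attrition rate to achieve a final number of 128 couples". It adds a second reason for enrolling more, "as well as the possibility that one member of a couple ends participation while the other continues", but puts no number on it. From these it concludes: "we estimate needing to enroll between 160-200 couples". It ends with a ceiling: "Therefore, we will enroll up to 200 mother-partner pairs during the study period". No other section explains the 60 or the 160.

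**The concern.** The paragraph holds two completer targets, 120 couples (2 x 60) and 128 couples (2 x 64). The one labelled as the minimum does not reach the paragraph's own figure for 80% power. That conflict needs no assumption about effect size, sidedness or attrition.

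The lower enrolment figure has the same weakness: at the attrition rate the plan itself ties to the 128, enrolling 160 gives 120. This paragraph is what a reader will use to judge whether recruitment succeeded. As written, 120 completing couples would both satisfy the minimum and miss the target. A team that stopped at 160 would be inside the written range and, at 25% attrition, below the size that the power statement calls for.

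**Working it through.** **Inputs from section II.A:** power 80%; alpha 0.05; 64 per arm required; minimum 60 couples per arm; attrition 25%; final number 128 couples; enrolment 160 to 200 couples.

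**Assumptions, because the documents are silent:** standardised difference d = 0.50; two-sided test; 1:1 allocation; the 60 per arm means completing couples, since enrolment is given separately; one mother analysed per completing couple. The plan says 64 participants in one place and 128 couples in the next, and the last assumption follows its final number.

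**1. Reproduce the 64.** For a two-sided, two-sample t-test at 0.05 with d = 0.50 and 80% power, the solution is n = 63.8 per arm, rounded up to 64. This matches the plan. A one-sided test gives about 50, and d = 0.6, 0.7 or 0.8 gives 45, 34 or 26, so none of these matches.

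**2. Attrition.** Completers = enrolled x (1 - 0.25); enrolment needed = target / (1 - 0.25).

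| Enrolled couples | Completing couples | Per arm | Against 128 |
|---|---|---|---|
| 160 | 160 x 0.75 = 120 | 60 | 8 short |
| 172 | 172 x 0.75 = 129 | 64.5 | met |
| 200 | 200 x 0.75 = 150 | 75 | met |

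Needed for 128: 128/0.75 = 170.7, so 171, or 172 for equal arms. The low end is therefore 11 to 12 enrolled couples short. Enrolling 160 is enough only if attrition is no more than 1 - 128/160 = 20%.

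The 160 equals 128 x 1.25, which is what results from adding 25% to the target instead of dividing by 0.75. It also equals 120/0.75. The text does not show which was used.

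**3. Power** (noncentral t, d = 0.50, two-sided 0.05, unadjusted).

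| Completers per arm | Power |
|---|---|
| 60 | 77.5% |
| 64 | 80.1% |
| 75 | 86.0% |

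The loss from 64 to 60 is 80.1 - 77.5 = 2.6 points. The difference detectable with 80% power moves from d = 0.499 to d = 0.516.

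**4. Loss of one member of a couple.** The plan does not say whether this comes on top of the 25%, or whether intact couples are needed. If both are so, the room left is 129 - 128 = 1 couple at 172 enrolled and 150 - 128 = 22 couples at 200 (22/150 = 14.7%). With an assumed further loss of 5%, 128/(0.75 x 0.95) = 179.6, so 180 couples. With 10%, 128/(0.75 x 0.90) = 189.6, so 190. Both lie within 200.

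**The case against.** The strongest reply is that the working number is sound. The plan is to enrol up to 200 pairs, which leaves 150 at 25% attrition; the correct 171 to 172 already lies inside the stated range; and nothing makes 160 a stopping point. This stands as a reason to call the point minor. It does not remove it, because a ceiling guarantees nothing and the only minimum the paragraph gives is 60 per arm.

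Other replies carry some weight:

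- **Adjustment for baseline.** Section II.E plans ANCOVA for the continuous outcomes. Taking the effective difference as d divided by the square root of (1 - r squared), with one degree of freedom fewer, power at 60 per arm is 79.2%, 80.1% or 81.3% for an assumed baseline-outcome correlation r of 0.20, 0.25 or 0.30. This could recover the loss, but the plan states no correlation and does not argue this way. Nor does it cover exclusive breastfeeding, a primary outcome that is to be analysed by logistic regression.
- **Effect size.** No value of d is given. At 60 per arm, power is 80.0% at d = 0.516, 84.8% at 0.55 and 90.3% at 0.60, so a slightly larger effect removes the loss. But d = 0.50 is the value that yields the plan's own 64.
- **Pilot retention.** The Introduction reports: "Follow-up rates at 6-weeks postpartum were 94% for mothers and 90% for partners". At those rates 160 couples would leave 160 x 0.90 = 144 to 160 x 0.94 = 150. However, the pilot enrolled 17 mothers and 10 partners, these are 6-week rates, and outcomes here run to 6 months. The plan chose 25%.
- **Mothers are not couples.** Breastfeeding status comes from mothers only, and a mother whose partner leaves can still supply it. If the 25% counts broken couples, 160 enrolled could leave more than 120 mothers, and 77.5% would understate power for the maternal outcomes. The plan does not say what the 25% counts.
- **Intention-to-treat with multiple imputation.** Section II.E specifies this, which softens the completer-based power figures. It does not change a target that the plan states as a final number after attrition.

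Reading the 60 as enrolled couples makes matters worse: 60 x 0.75 = 45 per arm, about 65% power at d = 0.50.

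**Conclusion.** The concern holds as a minor arithmetic inconsistency. The conflict between 60 and 64 per arm is plain on the page, and the shortfall at 160 follows from the plan's own 25%. The shortfall is 8 completing couples, or 11 to 12 enrolled couples, and it affects only the stated minimum and the low end of the range. The cost of about 2.6 points of power rests on d = 0.50, a two-sided unadjusted t-test and one mother per completing couple. A correlation of about 0.25 with baseline would offset it for the continuous outcomes. At 200 enrolled there is no shortfall.

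**What to change.** Use one completer target throughout the paragraph, and say whether the 25% counts mothers or couples.

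**Option A, which keeps 80% power.** Replace the minimum of 60 with 64 completing couples per arm (128 in total), and restate the range along these lines: *With 25% attrition alone, at least 172 couples are needed. We will enrol 172 to 200 couples; the margin above 172 is for couples in which only one parent stays in the study.* The sponsor should confirm that this is what the margin is for. The cost is a wording change and up to 172 - 160 = 12 more couples at the low end. Section II.D allows up to $150 in gift cards per couple, so that is at most 12 x $150 = $1,800, plus recruitment effort, all within the planned ceiling of 200.

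**Option B, which keeps the smaller size.** Keep 60 per arm and 160 enrolled, change the final number from 128 to 120, keep the statement about one parent leaving, and give the power at that size as about 77% to 78%. The sponsor should confirm the underlying d = 0.50 and two-sided test. This is a wording change only. Its drawbacks are a stated power below 80% at the minimum and no room at 160 for one-parent loss if that comes on top of the 25%, since 160 x 0.75 is exactly 120; the room up to 200 would have to cover it.

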Hypothesis 1: Participants randomly assigned to the intervention will report higher breastfeeding self-efficacy and exclusive breastfeeding at six weeks and six months postpartum compared to those assigned to usual care.

Aim 2: Assess whether improved coping with stress (as measured by self-reports), and partner support (as measured by partner and self-report) are mechanisms for the intervention.

Hypothesis 2: Participants randomly assigned to the intervention will report increased positive coping behaviors and higher perceived partner support at six weeks and six months postpartum compared to participants assigned to usual care.

Aim 3: Investigate relationships among levels of hair cortisol, stress (e.g. as indexed by subjective reports of stress) and resilience (social support and positive coping) factors.

Hypothesis 3: Hair cortisol levels measured immediately postpartum will be positively associated with symptoms of depression, anxiety, and stress, and negatively associated with perceived partner support and effective coping.

Aim 4: Investigate hair cortisol levels as a biological indicator of susceptibility (e.g. moderator) to intervention effects.

Hypothesis 4: Mothers who have moderate-high hair cortisol levels will benefit most from HHL.

C. Study Variables

A summary of the measures proposed is provided in the table below.

Construct	Measure	0-2 days postpartum		6 weeks postpartum		6 months postpartum	
		mom	partner	mom	partner	mom	partner
Breastfeeding	Index of breastfeeding status	x		x		x	
Self-efficacy	Breastfeeding self-efficacy scale short form	x	x	x	x	x	x
Coping Behavior	brief COPE	x	x	x	x	x	x
Partner Support	Postpartum Partner Support Scale	x	x	x	x	x	x
	Social provisions checklist	x	x	x	x	x	x

Mood/Stress	Edinburgh Postnatal Depression Scale	x	x	x	x	x	x
	Depression, Anxiety, and Stress Scale	x	x	x	x	x	x
	Maternal Mood Screener	x	x	x	x	x	x
Sleep Quality (cortisol covariate)	Pittsburgh Sleep Quality Index	x					
Acceptability & Adherence	HHL acceptability scale Participant adherence			x	x	x	x

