level that accurately described their breastfeeding behaviors within the previous 24 hours. Four levels will be reported: exclusive breastfeeding (breast milk only), partial breastfeeding (breast milk and at least 1 bottle of formula per day), token breastfeeding (breast given to comfort baby not for nutrition), and no breastfeeding. Higher values represent more exclusive breastfeeding. This measure has been successfully used at RMH in previous research (Henshaw et al, 2015).

Breastfeeding Self-Efficacy Scale-Short Form (McCarter-Spaulding & Dennis, 2010). The BSES-SF has demonstrated strong reliability and validity and will be used to measure BSE. Higher scores indicate greater self-efficacy related to breastfeeding. High internal consistency has been demonstrated in previous samples (Cronbach's $\alpha=.91$; (Henshaw et al., 2015). A wording change to measure self-efficacy in the supportive partner role has also been validated (Dennis, Brennenstuhl, & Abbass-Dick, 2018) and will be used for the partner survey.

Brief COPE. This 28-item validated scale derived from a previously published measure showing reliability (Cronbach's $\alpha=.62-.85$, test-retest $r = .46-.89$) and convergent validity with several established coping measures (Carver, Scheier, & Weintraub, 1989) will be used to identify coping strategies consistent with cognitive-behavioral skills, such as positive reframing, and absence of avoidance (Carver, 1997).

Pittsburgh Sleep Quality Index (PSQI). The PSQI assesses sleep quality, which is a critically important covariate of hair cortisol and mood. The PSQI is well-established questionnaire for assessing sleep quality, duration and disturbances. The PSQI shows good internal consistency Cronbach's $\alpha=.83$, test-retest reliability ($r = .85$) and predicted clinically determined poor sleepers at sensitivity of 89.6% and specificity of 86.5% (Buysse, Reynolds, Monk, Berman & Kupfer, 1989). The PSQI reliability and validity has been established with a pregnant sample as well (Skouteris, Wertheim, Germano, Paxton & Milgrom 2009). Unlike the other outcome measures, the Pittsburgh Sleep Quality Index is only measured at baseline.

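### Feeding status, a primary outcome, is reported only by the mother; adding the item to the partner's existing follow-up surveys would be a cheap aid to imputation

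*Combined protocol and SAP*

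**What the plan says.** All references are to the combined protocol and SAP.

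- **Outcome.** The Introduction names exclusive breastfeeding and breastfeeding self-efficacy, both at 6 weeks and 6 months, as primary.
- **Who reports feeding.** In the table of II.C Study Variables, the row "Index of breastfeeding status" is marked for the mother at all three times and is blank for the partner. II.C.1 Measures has women choose, from four levels, the "level that accurately described their breastfeeding behaviors within the previous 24 hours".
- **What the partner answers.** At both follow-ups the table gives the partner the self-efficacy scale (reworded for the supporting role), the coping scale, two support scales, three mood or stress instruments and the acceptability scale.
- **Who the partner is.** II.A Study Population requires the mother to be living with a partner or spouse at entry.
- **Attrition.** II.A sizes enrolment thus: "Assuming a conservative 25% attrition rate to achieve a final number of 128 couples". It adds "the possibility that one member of a couple ends participation while the other continues" and concludes "we estimate needing to enroll between 160-200 couples".
- **Missing data.** II.E Statistical Analysis plans an intent-to-treat analysis with multiple imputation and logistic regression for exclusive breastfeeding. It does not specify the imputation model.
- **Other feeding information.** The Intervention part of II.D describes a weekly yes/no text during the six-week program. Control group texts are described as not concerning breastfeeding.

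**The concern.** The plan foresees couples in which one member leaves, and it goes on surveying the one who stays. If the mother is the one who stops, the person still answering shared her household at entry and can probably say how the baby is fed, but the survey does not ask.

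No other planned source reports exclusivity. The weekly text cannot separate exclusive from partial feeding and ends at 6 weeks, so at 6 months there is no second source.

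The risk is bias more than precision. A mother who has stopped exclusive breastfeeding may be less willing to answer a breastfeeding survey, and the Intervention section itself anticipates guilt or distress on stopping. If silence depends on feeding status, imputation from other variables cannot detect it. A partner's report would give some evidence about those same mothers, and it cannot be collected afterwards.

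**Working it through.** **1. The plan's own sample size.** II.A claims "80% power to detect a medium-large effect in outcomes", which "should be achieved with 64 participants per arm", at α = 0.05. No numerical effect is given. Assume d = 0.5, two-sided.

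- Normal approximation: n = 2(1.960 + 0.842)²/0.5² = 62.8, so 63 per arm.
- Exact t-test: 63.8, so 64 per arm. The figure reproduces.
- Enrolment for 128 completers at 25% loss: 128/0.75 = 170.7, so 171. This lies inside the stated 160 to 200.

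**2. Effect for the binary outcome.** The only exclusive breastfeeding rate in the documents is 44.4% (US, three months; Introduction). Taking h = 0.5 as the counterpart of d = 0.5 gives p₂ = sin²[(2·arcsin√0.444 + 0.5)/2] = 0.689. Power is Φ(h√(n/2) − 1.96), with n per arm and 1:1 allocation assumed. With 128 couples (n = 64) it is 80.7%.

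**3. Mother-only loss at pilot rates.** The pilot (17 mothers, 10 partners, 6 weeks only) had 94% follow-up for mothers and 90% for partners. If the two are independent, mother missing with partner present = 0.06 × 0.90 = 5.4% of couples. The last column counts every such partner report as a full observation.

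| Enrolled | Mother-only loss | Mothers observed | Power without | Power with, at most |
|---|---|---|---|---|
| 160 | 8.6 | 150.4 | 86.6% | 88.4% |
| 171 | 9.2 | 160.7 | 88.7% | 90.3% |
| 200 | 10.8 | 188.0 | 92.9% | 94.1% |

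The gain is one to two points at most. If each report is worth r² = 0.8² = 0.64 of an observation (r assumed), power at 171 becomes 89.7%, a gain of about one point.

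**4. A much less favourable scenario.** Suppose 171 couples enrol and 25% of mothers are missing (171 − 128 = 43), and a share f of their partners answer. The documents do not give f. Effective couples = 128 + 43·f·w, with w = 1 for perfect agreement and w = 0.64 for r = 0.8.

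| f | Couples, w = 1 | Power | Couples, w = 0.64 | Power |
|---|---|---|---|---|
| 0 | 128.0 | 80.7% | 128.0 | 80.7% |
| 0.25 | 138.75 | 83.8% | 134.9 | 82.7% |
| 0.50 | 149.5 | 86.4% | 141.8 | 84.5% |
| 0.75 | 160.25 | 88.6% | 148.6 | 86.2% |

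The w = 1 columns are ceilings. They treat the partner's answer as the outcome, whereas an auxiliary variable yields less.

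**The case against.** Much of the case against stands.

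- **Attrition wording.** A reader might take the 25% to be missing mothers, many with a responding partner. II.A states it for couples, lists one-member dropout separately as a possibility, does not say which member leaves and gives no rate. Step 4 is therefore a scenario and not the plan's forecast.
- **Power is already padded.** At 200 enrolled with 25% of mothers lost, 150 are observed and power is about 86%. Padding does nothing about bias, however.
- **Other auxiliaries exist.** A reader might infer that imputation would rest on baseline and arm only, leaving feeding wholly unknown. II.E does not say so. Six-week feeding status could inform six months, and the partner's self-efficacy score and some weekly replies could also enter. None reports exclusivity at the time in question.
- **Timing and co-residence.** A same-day report cannot be assumed, because the surveys are emailed links and the index covers 24 hours. Living together is an entry criterion only.
- **Error by arm.** Intervention partners receive texts encouraging them to support breastfeeding, so their error may differ from that of control partners. Carrying agreement over from responding couples to silent mothers is itself a missing-at-random assumption.
- **Consent.** If ending participation means full withdrawal, collecting a mother's feeding data through her partner is not acceptable without more.

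Maternal self-report is a coherent choice, used before at the main site, and the plan does not contradict itself here. These points limit the size of the gain and shape the fix. They do not show that leaving the item out has any advantage while the mother's report remains the outcome.

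**Conclusion.** The point holds as a cheap improvement, not as an error. Feeding status has one informant although a second is surveyed at both follow-ups, and for a mother-only non-response nothing else planned reports exclusivity at that time.

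Its size cannot be settled from the documents. It is about 5% of couples and one to two points of power at most if the pilot's 6-week rates held and responses were independent; positive correlation within couples would make it smaller, and 6-month rates are unknown. It is larger only if mother-only silence is common.

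A reader might infer that the item would halve the missing data, for example from 43/171 = 25.1% to 21.5/171 = 12.6% at f = 0.5, and shrink worst-case bounds to match. That counts partner answers as observed outcomes and rests on a mother-only loss that the plan does not state.

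The main benefit is weaker dependence on missing-at-random for feeding status. Maternal self-efficacy, the other primary outcome, cannot be recovered this way.

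**What to change.** 1. In the II.C table and II.C.1, add the four-level feeding index to the partner's 6-week and 6-month surveys.
2. In II.E, state that the partner's report enters the imputation model for the mother's feeding status as an auxiliary variable only, with arm and an arm-by-partner-report term. The mother's own report is the outcome whenever present.
3. Report mother-partner agreement by arm in couples where both answer.
4. Add a sensitivity analysis that imputes without the partner report.
5. State that the partner's report is not used for a mother who has withdrawn consent, as distinct from one who did not answer or only unsubscribed from messages.

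The cost is one extra item in two existing REDCap surveys, a small amendment and a few sentences in II.E. The remaining drawback is that partner reports may be less accurate and may err differently by arm; items 2 to 4 are there to contain and expose that.
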